# 2. LAY SUMMARY

Around 1 in 10 of all people attending hospital with a broken bone have injured their ankle joint. Most of these injuries occur in people aged 50 years and over as a result of a fall from a standing height. After a broken ankle is treated with or without surgery, the ankle is kept still in a boot or cast for around six weeks. Keeping the ankle still protects it as it heals but causes stiffness and weakness. Putting weight through the ankle after the boot or cast is removed is difficult. People often feel unsteady and lack confidence. At this time, health care professionals are recommended to provide advice on early ankle exercises and on how to gradually return to daily life.

After this initial advice, there is no national guidance on whether further rehabilitation under the supervision of a physiotherapist should be provided. Previous research in younger adults found additional physiotherapy did not improve recovery, but it is not clear whether older adults would benefit. Extra sessions of physiotherapy can be difficult for patients to attend and are costly to the health service.

Our study will find out if referral for physiotherapy appointments after a person over 50 years has suffered a broken ankle helps them recover quicker and better when compared to good quality advice on self-management which includes booklets and videos.

To compare the two treatments properly 344 people will be recruited to take part. Participants will be placed by chance into one of two groups by a computer program, this will make sure that the groups are similar and the comparison is fair. Over a 6-month period participants will be asked about their health, walking ability and other daily activities, as well as any complications and specific costs.

A small version of this study was conducted to improve the design. We used feedback from health professionals and patients who took part. This project was developed by and will be run by a team of patient representatives, clinical experts in trauma rehabilitation and orthopaedic surgery, study management specialists, and experienced statisticians.

The Oxford Clinical Trials Research Unit, based within the University of Oxford, will support the study. Monitoring committees of patient representatives and independent experts will oversee the safety of participants and the progress and conduct of the study.

Findings of the research will be published so that it is free to access in scientific journals and shared at conferences. Our Patient and Public Involvement research team member will support development of lay summaries and will be actively involved in reaching patient networks.

Clinical Research Protocol Template version 15.0

### CONFIDENTIAL

© Copyright: The University of Oxford and Oxford University Hospitals NHS Foundation Trust 2019 Page 7 of 39

## 3. SYNOPSIS

Study Title	Effectiveness of supervised versus self-directed rehabilitation for people aged 50 years and over with ankle fractures: the AFTER trial		
Internal ref. no. / short title	AFTER		
Study registration		en registered with the curren erence number ISRCTN XXXXXX	t controlled trials
Sponsor	University of Oxfor	d	
Funder	National Institute f	or Health Research	
Study Design	Multicentre randor	mised parallel-group superiority	trial
Study Participants	Adult patients ageo	1 50 years and over with ankle fr	actures
Sample Size	344		
Planned Study Period	September 2021 – July 2024		
Planned recruitment period	March 2022 – June 2023		
	Objectives	Outcome Measures	Timepoint(s)
Primary	Ankle Function	Olerud and Molander Ankle Scale (OMAS)	6 months post- randomisation
Secondary	Ankle Function	OMAS	Baseline, 2 and 4 months post- randomisation
	Health-related quality of life	EQ-5D-5L	Baseline, 2, 4 and 6 months post- randomisation
	Pain	Pain sub-scales of the EQ-5D- 5L and OMAS	Baseline, 2, 4 and 6 months post- randomisation
	Physical Function	PROMIS Physical Function	Baseline, 4 and 6 months post- randomisation
	Self-efficacy	Self-Efficacy Exercise Score	Baseline, 4 and 6 months post- randomisation

Clinical Research Protocol Template version 15.0

CONFIDENTIAL

	Exercise adherence	Self-reported exercise frequency	2, 4 and 6 months post- randomisation
	Complications	Complications Questionnaire and Case Report Form	2, 4 and 6 months post- randomisation
	Cost effectiveness	Health economics questionnaire	2 and 6 months post- randomisation
Intervention	Supervised rehabilitation		
Comparator	Self-directed rehabilitation		

### 4. ABBREVIATIONS

AE	Adverse Event
AFTER	Ankle Fracture Treatment: Enhancing Rehabilitation trial
CACE	Complier Average Causal Effect
CAT	Computer Adaptive Test
CHEERS	Consolidated Health Economic Evaluation Reporting Standards
CI	Chief Investigator
CONSORT	Consolidated Standards of Reporting Trials
CRF	Case Report Form
DMP	Data Management Plan
EQ-5D-5L	EuroQol 5 Dimensions – quality of life questionnaire
GCP	Good Clinical Practice
HRA	Health Research Authority
HRQoL	Health Related Quality of Life
НТА	Health Technology Assessment
ICER	Incremental Cost-effectiveness Ratio
ICF	Informed Consent Form
ID	Identity
IP	Intellectual Property
IRAS	Integrated Research Application System
IRT	Item Response Theory
ISRCTN	International Standard Randomised Controlled Trial Number
ITT	Intention-to-treat
NDORMS	Nuffield Department of Orthopaedics, Rheumatology and Musculoskeletal Sciences
NHS	National Health Service
NIHR	National Institute for Health Research
NICE	The National Institute for Health and Care Excellence
OCTRU	Oxford Clinical Trials Research Unit
L	

Clinical Research Protocol Template version 15.0

© Copyright: The University of Oxford and Oxford University Hospitals NHS Foundation Trust 2019 Page 10 of 39

	·
OMAS	Olerud and Molander Ankle Scale
Ы	Principal Investigator
PIS	Participant Information Sheet
PPI	Patient and Public Involvement
PROM	Patient Reported Outcome Measure
PROMIS	Patient-Reported Outcomes Measurement Information System
PSS	Personal Social Services
QALY	Quality Adjusted Life Year
RCT	Randomised Controlled Trial
REC	Research Ethics Committee
REDCap	Research Electronic Data Capture
RfPB	Research for Patient Benefit
RGEA	Research Governance, Ethics & Assurance Team
SAE	Serious Adverse Event
SAP	Statistical Analysis Plan
SEE	Exercise Self-efficacy
SFQ	Site Feasibility Questionnaire
SOPS	Standard Operating Procedures
TIDieR	Template for Intervention Description and Replication
TMG	Trial Management Group
тос	Trial Oversight Committee
υк	United Kingdom
UKCRC	UK Clinical Research Centre
URL	Uniform Resource Locators
US	United States
VAS	Visual Analog Scale

Clinical Research Protocol Template version 15.0

### 5. BACKGROUND AND RATIONALE

### What is the problem being addressed?

Ankle fractures are very common, accounting for 9% of all fractures managed in secondary care. (1) In the UK, incidence of these fractures is highest in people aged 50 years and over, peaking at 16 per 10,000 person-years in women aged 60 to 70. (2) As the population ages, a three-fold increase in these fractures is projected over the next two decades. (3) The mechanism of injury for people aged over 50 is usually a fall from standing height; the fracture is then defined as a fragility fracture. (4)

Treatments for ankle fractures range from conservative plaster casts or boots to surgical fixation. Our recent HTA-funded trial including adults aged 60 years and over found that, regardless of the initial fracture management, post-injury reduced ankle function and walking abnormalities remain at 6 months post-injury.(5, 6) Participants reported an average 30% loss of pre-injury ankle function. Function is poor due to pain, reduced joint motion,(7) lower limb muscle strength deficits,(8) gait abnormalities,(9) and resultant mobility limitations.(7, 10)

Weight bearing and ankle movement restrictions are usually lifted by the orthopaedic team six weeks after injury. At this stage, national guidance is that patients should be given advice on simple exercises and gradually resuming usual activities.(11) Advice is provided face-to-face in a fracture clinic and is sometimes supplemented by an information booklet.

Data from 24 UK hospitals indicated that, in addition to this advice, about two thirds of patients were referred to see a physiotherapist in an outpatient clinic for supervised rehabilitation.(5) Referral patterns varied both within and between hospitals; at some centres few patients were referred, while at others the majority receive 4 to 6 sessions of physiotherapy over several months.(5) The variation reflects that referrals are currently being made based on local practice or clinical opinion due to a lack of robust evidence to inform national guidance.

A James Lind Priority Setting Partnership on lower limb fragility fractures ranked 'What is the best physiotherapy and/or occupational therapy regime for adults during out-of-hospital recovery from a fragility fracture of the lower limb?' as second in the top ten, highlighting the importance of this research to clinicians, patients and carers.(12) Ankle fractures have a substantial impact on people's lives, resulting in mobility problems and reduced independence, and prognosis worsens with increasing age.(13) It is uncertain why people fare worse as they age but lower physiological reserves, comorbidities, reduced muscle mass and power (sarcopenia), and balance impairments are likely to contribute.(14) The resultant disability after injury has a significant associated socioeconomic burden, impacting on an individual's capacity to work, care for others, and perform daily activities.(5)

Clinical Research Protocol Template version 15.0

### CONFIDENTIAL

Physiotherapy after ankle fracture aims to support patients during the recovery period and provide individualised progressive exercise to improve muscle strength, range of motion, gait and balance. However, as physiotherapy is not without patient and health service burden and costs, it is important that the clinical and cost-effectiveness of physiotherapy-supervised rehabilitation is compared with good quality self-management advice. If superiority of physiotherapy is not demonstrated, this would support disinvestment in routine physiotherapy in this population, and support widespread implementation of a standardised self-directed rehabilitation intervention.

A Cochrane review in 2012 of ankle fracture rehabilitation concluded that there was insufficient evidence regarding physiotherapy after ankle fracture.(15) Our updated searches identified just one new study, the EXACT trial (n=213), which reported no differences in lower limb function between supervised exercise and one-off advice for adults with ankle fractures.(16) While this trial certainly adds to the body of evidence in this area of research, the vast majority of patients (>70%) were younger than 50 years of age, and in the group allocated to basic advice, about 39% sought additional out-of-trial physiotherapy. In the proposed study we will focus on patients aged 50 years and over to allow clinical practice in this patient population to be informed by appropriate evidence. In adults aged 50 years and over, experience of losing confidence and fear of future injuries are common after ankle fracture.(5, 6) There is also good evidence that progressive exercise reduces risk of falls in other clinical populations.(17) A tailored progressive exercise intervention supervised by a physiotherapist therefore has the potential to improve recovery in this older group, where rehabilitation needs are often more complex.

We have conducted a feasibility RCT(18) that informed the design of this definitive trial. We have conducted a programme of research with stakeholders from clinical practice, research, and patient and public involvement representatives from the UK Musculoskeletal Trauma PPI Group to optimise a physiotherapist-supervised rehabilitation intervention and self-directed rehabilitation intervention.

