## 6. OBJECTIVES AND OUTCOME MEASURES

The aim of this pragmatic, parallel-group, randomised controlled superiority trial is to evaluate the clinical and cost-effectiveness of supervised versus self-directed rehabilitation in improving ankle function for people aged 50 years and over with ankle fractures.

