## 7. STUDY DESIGN

AFTER is a multi-centre, parallel-group, superiority individually randomised controlled trial assessing the clinical effectiveness of supervised versus self-directed rehabilitation in improving ankle function for people aged 50 years and over after an ankle fracture. The trial will be conducted at secondary care trauma departments in a minimum of 20 NHS hospitals and their related physiotherapy services.

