# 11.2. Sample Size Determination

292 (146 per arm) participants providing primary outcome data at 6 months are required to detect a difference of 8 points on the OMAS score with an estimated standard deviation of 21 with 90% power and 5% (2-sided) significance. The minimum clinically important difference for the OMAS selected in surgical trials has usually been 10 points but for this trial of physiotherapy we have chosen a smaller difference of 8 points, which is likely to be clinically important and was supported by our patient advisory group. The chosen standard deviation of 21 is based on the AIM trial (6) (SD 21.7) and the feasibility study data (SD 20.5 based on 32 participants having reached the 6 month time-point - unpublished). This equates to a standardised effect size of 0.38, a small to moderate effect. In the AFTER feasibility study there was 11% loss to follow-up (those not providing the primary outcome data). In order to allow for potential loss to follow-up of participants in the definitive trial we have inflated the sample size by 15% to 344 participants (172 per arm).

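### The Background reads a failure to show superiority as support for disinvestment, although a non-significant result could still be compatible with the 8-point benefit the protocol calls important

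*Protocol*

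**What the plan says.** Section 5 of the protocol sets out what would follow from a result that does not favour supervised rehabilitation: "If superiority of physiotherapy is not demonstrated, this would support disinvestment in routine physiotherapy in this population". The same sentence adds that such a result would also support wide implementation of the self-directed programme.

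Section 6 describes the study as a "pragmatic, parallel-group, randomised controlled superiority trial", and section 7 repeats the superiority design. No equivalence or non-inferiority margin is given.

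On the size of effect that matters, section 11.2 says "we have chosen a smaller difference of 8 points, which is likely to be clinically important and was supported by our patient advisory group". The sample size is set to detect that difference "with an estimated standard deviation of 21 with 90% power and 5% (2-sided) significance".

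Sections 11.4 and 11.5 promise the adjusted mean difference at 6 months with a 95% confidence interval. Section 11.8 plans a cost-effectiveness analysis against stated thresholds per QALY. Neither the interval nor the economic result is made a condition of the disinvestment reading in section 5.

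**The concern.** The condition in section 5 is that superiority has not been demonstrated. Two different results meet it. In one, the interval lies wholly below 8 points, so an important benefit has been excluded. In the other, the interval contains both 0 and 8, so the trial has not settled the question. As worded, both support the same conclusion.

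The protocol's own account makes this matter. Section 5 reports that about two thirds of patients in UK hospital data were referred to physiotherapy, and section 9.6 calls referral the most common current standard of care. The sentence therefore concerns withdrawing something widely used. Section 9.6 also leaves usual physiotherapy available outside the trial intervention, and section 5 notes that about 39% of the advice group in an earlier trial sought it. Such use could dilute the contrast between arms and weaken a non-significant result further as evidence that no important benefit exists.

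**Working it through.** **Inputs (section 11.2):** target difference 8 OMAS points; SD 21, drawn from values of 21.7 and 20.5; two-sided 5% significance; 90% power; 146 evaluable per arm; 15% loss to follow-up. Allocation is 1:1 (section 9.4).

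**Reproducing the plan's figure.** The normal approximation gives n = 2 × (1.960 + 1.282)² × 21² / 8² = 144.8, so 145 per arm. The t-based calculation gives 90.04% power at 146 per arm, so 292 is right. Then 292 / 0.85 = 343.5, rounded up to 344. The sample size is sound.

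**Precision at the planned size, unadjusted.**
- SE = 21 × √(2/146) = 2.458.
- 95% half-width = t(0.975, 290 df) × 2.458 = 4.838.

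**The ambiguous zone.** Superiority is not shown if the estimate is below 4.838. The upper limit reaches 8 if the estimate is at least 8 − 4.838 = 3.162. Estimates from about 3.2 to 4.8 therefore meet both conditions. For example, an estimate of 4.0 gives an interval of −0.8 to 8.8.

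**Probability of landing in the zone** (normal approximation with the half-width held fixed):
- True difference 0: Φ(4.838/2.458) − Φ(3.162/2.458) = 0.975 − 0.901 = about 7%.
- True difference 8: the same by symmetry, about 7%.
- True difference 4: 2 × Φ(0.838/2.458) − 1 = about 27%.

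Using 1.96 in place of the t multiplier gives 7.3% and 26.1%.

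**What the present wording does at a true 8 points.** Superiority is missed with probability Φ((4.838 − 8)/2.458) = about 10%, and every such miss would support disinvestment. In about 7.5/9.9 = 75% of those misses the interval still contains 8.

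**What an interval condition does.** If the upper limit must be below 8, the probability of supporting disinvestment at a true 8 points is Φ((3.162 − 8)/2.458) = about 2.5%. At a true difference of 0, the probability of excluding 8 is Φ(3.162/2.458) = about 90%.

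**Sensitivity of the zone:**

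| Assumption | Zone (OMAS points) |
|---|---|
| SD 20.5, 146 per arm | 3.3 to 4.7 |
| SD 21, 146 per arm | 3.2 to 4.8 |
| SD 21.7, 146 per arm | 3.0 to 5.0 |
| SD 21, no loss (172 per arm) | 3.5 to 4.5 |
| SD 21, 146 per arm, assumed baseline–outcome correlation 0.3 | 3.4 to 4.6 |
| SD 21, 146 per arm, assumed correlation 0.5 | 3.8 to 4.2 |

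The last two rows multiply the SD by √(1 − r²). The zone closes when the half-width falls to 4, which needs r of about 0.56. The protocol gives no correlation.

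**The case against.** The strongest reply is that the sentence belongs to the rationale and is not an analysis rule. Section 11 contains no such rule, the primary objective is to quantify the difference and draw inferences, and the 95% interval will be published, so readers can see whether 8 lies inside it. To say that a result would support disinvestment is weaker than to say it would establish the case. For a service that carries cost and burden, it can also be a judgement about where the burden of proof lies. The economic analysis will supply evidence that does not depend on OMAS significance.

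Much of this stands, and it limits the point. A reader might infer that the protocol fixes a formal decision rule, or that it would report a non-significant result as no benefit. The text supports neither: the sentence is a Background statement of intended interpretation, and it does not claim equivalence. A reader might also take as the measure of the problem the chance of non-significance at smaller true benefits, about 47% at 5 points and 32% at 6. Those benefits lie below the trial's own target, and the 10% at 8 points is simply the type II error of a 90%-power design. Finally, the zone above is unadjusted, whereas section 11.4 plans adjustment for baseline OMAS and use of the intermediate time points.

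The reply does not remove the inference itself. Section 5 makes disinvestment depend on neither the interval nor the economic result, and it is the only place where the protocol says what a non-superior result would mean. Because the sentence is stated in the protocol, it is not a detail left to the SAP.

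**Conclusion.** The point holds as a moderate correction to the stated interpretation. It is not a defect in the sample size, the primary analysis or the conduct of the trial. In the unadjusted calculation at 146 per arm and SD 21, estimates of about 3.2 to 4.8 points would meet the section 5 condition while remaining compatible with the difference that section 11.2 treats as likely to be important. The probability is about 7% at a true difference of 0 or 8 and about 27% at 4. These figures rest on the planning SD, the planned loss to follow-up and no covariate adjustment. Adjustment would narrow the zone, and might close it, but the protocol lacks the correlation needed to say by how much.

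**What to change.** Reword the sentence in section 5 along these lines: the clinical case for disinvestment would be supported only if the upper limit of the 95% confidence interval for the 6-month OMAS difference (supervised minus self-directed) is below 8 points, read alongside the planned cost-effectiveness result; a non-significant result whose interval includes 8 points will be reported as inconclusive.

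The cost is wording only. The sample size stays at 344, since the planned 292 evaluable participants already give about a 90% chance of excluding 8 points if the true difference is 0. The downside is that some non-significant results must be called inconclusive, with the probabilities shown above.

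The threshold of 8 is the protocol's own figure. An estimate of 3.1 (interval about −1.7 to 7.9) would just satisfy it, so the trial team should confirm that it accepts 8 points as the benefit to be excluded.

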## 6. OBJECTIVES AND OUTCOME MEASURES

The aim of this pragmatic, parallel-group, randomised controlled superiority trial is to evaluate the clinical and cost-effectiveness of supervised versus self-directed rehabilitation in improving ankle function for people aged 50 years and over with ankle fractures.

## The primary objective is:

To quantify and draw inferences on differences in ankle function at 6 months postrandomisation between the trial intervention groups (supervised vs self-directed rehabilitation).

Clinical Research Protocol Template version 15.0

CONFIDENTIAL

© Copyright: The University of Oxford and Oxford University Hospitals NHS Foundation Trust 2019 Page 13 of 39

## The secondary objectives are:

To quantify and draw inferences on differences in:

- ankle function at 2 and 4 months
- ankle pain at 2, 4 and 6 months
- health-related quality of life (HRQoL) at 2, 4 and 6 months
- physical function at 4 and 6 months
- self-efficacy to exercise at 4 and 6 months
- exercise adherence at 2, 4 and 6 months
- risk of related complications over the initial 6 months
- cost-effectiveness of the interventions at 2 and 6 months

Outcomes	Objectives	Instruments	Timepoints
Primary	Ankle Function	Olerud and Molander Ankle Scale (OMAS)	6 months
Secondary	Ankle Function	OMAS	Baseline, 2 and 4 months
	Health-related quality of life	EQ-5D-5L	Baseline, 2, 4 and 6 months
	Pain	Pain sub-scales of the EQ-5D- 5L and OMAS	Baseline, 2, 4 and 6 months
	Physical Function	PROMIS Physical Function	Baseline, 4 and 6 months
	Self-efficacy	Self-Efficacy Exercise Score	Baseline, 4 and 6 months
	Exercise adherence	Self-reported exercise frequency	2, 4 and 6 months
	Complications	Complications Questionnaire and Case Report Form	2, 4 and 6 months
	Cost effectiveness	Health economics questionnaire	2 and 6 months

### Table 1: Assessments performed to enable delivery of objectives:

## 6.1. Outcome measures

The primary outcome is patient-reported ankle-related symptoms and function at 6 months after randomisation measured by completion of the Olerud and Molander Ankle Score (OMAS).(19) The OMAS is a 9-item questionnaire which is completed directly by the participant (0-100, with higher scores indicating better function). The OMAS has been the primary outcome for a number of other ankle fracture trials, including NIHR HTA trials.(5, 20)

Clinical Research Protocol Template version 15.0

